9.2. COSMOS Cancer Tissue Study

We plan to establish a biobank of tumor tissue and slides for the future examination of the mechanistic effect, if any, of multivitamin and cocoa flavanol use on risk and survival from common cancers, such as breast, bladder, prostate, and lung, among the COSMOS population. The COSMOS trial provides a unique and cost-efficient resource to elucidate the molecular mechanisms by which the study supplements exert their benefit(s). We plan to examine the biologic effect of multivitamins and cocoa flavanols by leveraging cutting-edge molecular and genomic technologies (including but not limited to immunohistochemistry, RNA-sequencing, whole genome sequencing, epigenomic assays) to better understand cancer etiology.

To determine the feasibility of establishing a biobank of cancer tissue, we plan to conduct a pilot study to assess willingness of COSMOS participants to provide consent for their tissue samples to be collected and the success of obtaining tissue blocks and/or slides from hospitals and providers' offices. We will request samples only from those participants who have confirmed diagnoses of incident cancers. As per study protocol, we will first request consent to review medical records from participants who self-report a new or recurrent cancer diagnosis on the periodic COSMOS health questionnaires. For those who provide consent, we will obtain the relevant medical records from treating physicians or healthcare facilities. Once the records are received, reviewed by COSMOS investigators, and the diagnoses are confirmed, we will send participants a letter to request their tissue samples. Our goal is to conduct the pilot study in a sample of up to 80 participants with confirmed cases of incident cancers.

9.3 Coronavirus disease 2019 (COVID-19)

In response to the coronavirus disease 2019 (COVID-19) pandemic, we will send COSMOS participants email invitations for online REDCap surveys that have been prepared to collect critically needed, time-sensitive data on the epidemiology of COVID-19 in older adults, who have been disproportionately affected by the ongoing pandemic.

COSMOS participants will be combined with participants in two other active, large-scale, long-term prospective studies conducted at our Division of Preventive Medicine, the VITamin D and Omega-3 Trial (VITAL) (protocol #2009P-001217), and the Women's Health Study (WHS) (protocol #2004P-001661), for a total of 52,000 participants who will be sent the email invitation with the secure link to the COVID-19 survey. Participants in these three studies have demonstrated interest, dedication, and continued participation in medical research and disease prevention through the completion of questionnaires and other study activities.

Participants who provided email addresses and have indicated willingness to be contacted by email to complete surveys online will be sent the invitation with the secure link to the COVID-19 survey. We will send reminder emails to non-respondents. The survey is consistent with our REDCap surveys sent and completed in the past and will collect critically important and time-sensitive information about symptoms, testing, diagnoses, treatments, severity of illness, and risk factors for the coronavirus. If willing, anyone who reports having the coronavirus infection and/or COVID-19 hospitalization will be contacted to provide consent to review their medical records following standard procedures already in place for the study.

COVID-19 surveys will be sent at three different time points spaced approximately one month apart to update participant status with regard to coronavirus testing, symptoms, diagnoses, and other relevant risk factors during this evolving pandemic. The data from these COVID-19 surveys will make seminal contributions to our understanding of the causes and consequences of coronavirus infection and COVID-19 during this pandemic.

COVID-19 is an ongoing global pandemic currently affecting the US, yet little is known about risk factors for illness, including more severe illness and indicators of recovery. COSMOS will collaborate with the **Researching COVID to Enhance Recovery (RECOVER)** study, a National Institutes of Health (NIH) COVID-19 Initiative Project to address this issue. COSMOS will send an initial email to inform participants about this new research opportunity. Participants that are interested to learn more about the RECOVER study have the option to click on a secure REDCap link to view the invitation letter and brief screening survey. The COSMOS group will identify eligible and willing participants, and their screening information will be sent to the RECOVER group through a secure MGB server.

10.0. Statistical Analysis

In this 2x2 factorial trial, the primary aim is to compare the main effects of intention-to-treat with cocoa extract on incident CVD events, and multivitamins on rates of diagnoses of new cancers. The primary analysis will be based on the intention-to-treat principle and use the Cox proportional hazards model for time-to event data⁴¹ and estimate the HR for each intervention using indicators for the specific treatment, controlling for the second intervention, and stratifying the baseline hazard by (at minimum) sex, age group, and recruitment center (WHI or BWH). P-values will be based on a score tests for each intervention hazard ratio. Because the cohort consists of older women and men, competing risks due to deaths from other causes will be also be incorporated. Specifically, the primary analyses will estimate the cause-specific hazard and HR comparing intervention groups for each outcome by censoring individuals with deaths due to competing causes. We will estimate the cumulative incidence function for each comparison (multivitamin versus placebo, cocoa flavanols versus placebo) and plot the subdistribution of each endpoint over time.^{42,43}

The alternative Fine and Gray approach⁴⁴ models the effect of treatment on the subdistribution hazard or directly on the cumulative incidence function. Although we will consider this model, Cox proportional hazards will be our primary analysis. Additional analyses of composite endpoints that include total mortality will provide a practical approach to the evaluation of the impact of competing risks.

In secondary analyses, we will examine effect modification by the other randomized intervention, gender, age, other key risk factors, time, and concomitant medications such as statins and aspirin. Interactions will be interpreted cautiously as hypothesis generating. We will also stratify by past randomization status in WHI trials. We will also consider baseline dietary intake and a subcohort of women and men with biomarker data analyzed as a case-cohort study using methods for proportional hazards regression.⁴⁵ Because of frequency matching by age, we will use appropriate stratum-specific weighting of observations.⁴⁶

11.0. Data Management

The COSMOS data repository will be a single centralized database maintained by BWH

All pre-randomization participant data collected from all BWH participants and WHI participants who signed a COSMOS consent form are stored on the BWH data systems. Prior to the 12-month post-randomization phase, follow-up for missing and incomplete information is done by each institution separately but the data are stored centrally at BWH. Secure file transfer protocols are used to share data between the two institutions. Eligibility assignment during pre-randomization is performed by the WHI CCC for each participant and the data is transferred back to BWH securely.

Separate web applications at each institution allow their respective staff to perform the necessary tasks. The CCC will implement systems to support recruitment and screening mailings, data entry, and scanning of forms for WHI participants who enroll into COSMOS; modify the outcomes processing system to accommodate

changes in outcomes collection required for WHI participants; and create datasets and reports to support study monitoring and analyses. BWH will be responsible for recruitment and screening of BWH participants; scanning of BWH forms; ancillary study and biospecimen project mailings; post-randomization form mailings beginning with the 12-month follow-up phase; and study pill dispensing. The CCC will support BWH's participant unblinding efforts and create final datasets for analyses and data sharing purposes.

Starting in September 2016, some study data will be collected electronically using REDCap (Research Electronic Data Capture), a free, secure, HIPAA-compliant web-based application hosted by the Partners HealthCare Research Computing, Enterprise Research Infrastructure & Services (ERIS) group. Vanderbilt University, with collaboration from a consortium of academic and non-profit institutional partners, has developed this software and workflow methodology for electronic collection and management of research data. Our research team will develop REDCap surveys that mirror the standard paper-based questionnaires used throughout the trial. REDCap provides features that can be used for a variety of research projects and provides an intuitive interface to enter data with real-time validation (automated data type and range checks). The system offers easy data manipulation with audit trails, reports for monitoring and querying participant records, and an automated export mechanism to common statistical packages (e.g., SAS).

Participants' names and contact information will be accessible only to staff members who need the information for their jobs. Endpoint and health-related questionnaire data will be stored in separate files from the processing data and will be accessible only to approved investigators and programmers. In these files, participants are identified only by study ID.

11.1 Sending Data/Materials to Research Collaborators outside Mass General Brigham

A deidentified data set will be sent to [name], a retired professional data analyst, for dementia research. The data sent will contain deidentified variables from the COSMOS Mind ancillary study tests outlined in Section 9.1. The data will be securely transferred using the Partners Secure File Transfer system.

Limited data sets will be sent to [name] at Penn State College of Medicine in Hershey, Pennsylvania and [name] at the National Cerebral and Cardiovascular Center in Suita, Japan for data analysis purposes. The data sets will contain descriptive, adherence, and outcome variables. The data will be securely transferred using the Partners Secure File Transfer system.

12.0. Study Monitoring

An independent Data and Safety Monitoring Board (DSMB) for COSMOS will be convened with appropriate expertise in clinical trials, epidemiology, biostatistics, and relevant clinical areas such as CVD and cancer. Representatives from the VITAL DSMB and the parallel WHI oversight committee (currently the DSMB) will be invited to participate.

The role of the COSMOS DSMB will be to examine the unblinded data on adherence, endpoints and adverse effects and recommend continuation, alteration in study design, or early termination as appropriate to assure the ethical conduct of the study.

Interim trial results will be assessed with the Haybittle-Peto rule,^{47,48} adjusting for multiple looks. In this method, interim results are compared to a z-score of 3 standard deviations ($p=0.0027$) throughout the trial. The final results may then be interpreted as having close to nominal significance levels. This rule appropriately requires very strong evidence for early stopping, is more conservative than the Pocock⁴⁹ and O'Brien-Fleming⁵⁰ rules

and the alpha-spending function,⁵¹ and can be conducted at convenient times without inducing statistical complexity.⁵²

While these rules are intended for the primary endpoints, the goal is to assess the overall balance of benefits and risks of the two agents. Thus, consideration will also be given to the secondary endpoints that are needed in the interpretation of overall results. The monitoring rules will serve as guidelines in evaluating the strength of the existing data regarding benefits and harms. All decisions for continuation or stopping of treatment arms must be made after examining the totality of evidence, including other trial data, on these agents. Each treatment arm comparison will be considered independently of the other, i.e., one intervention may be stopped while the other may continue without any disruption in the planned follow-up.

13.0. Quality Assurance

Redundancies will be built into the data processing systems to ensure accurate recording of data and proper follow-up. All research forms will be scanned in and the data read by a character-recognition software program (Cardiff TeleForm). Inconsistent, and unclear data will be reviewed by a verifier who will edit misread variables. Information from forms that cannot be scanned will be copied onto new forms. The new data forms will be scanned and the original, damaged forms will be filed for future reference, if necessary. All data will undergo additional within-form and across-time checks to verify accuracy. Following data entry, all questionnaire responses that require additional follow-up for missing data, participant comments on the form or for endpoint validation will be manually reviewed to ensure correct processing and accurate follow-up.

Great care will be taken to ensure that participants receive their randomly assigned drugs. Upon receipt of drug shipments from the manufacturer, each of the four drug groups will be stored in segregated areas. A random sample of drugs bottles or calendar packs will be pulled from each drug group and blindly tested to insure that the packaged contents match the study label. At the time of packaging for shipment to individual participants, listings will be divided according to drug group assignment and only one group will be packaged at a time. The packaging area will be cleaned and cleared prior to packaging and shipment of the next drug group. If drug packages are returned by the postal service as undeliverable or declined by a participant, the contents of the package will be blindly tested as an additional level of quality control.

14.0. Study Administration and Organization

The BWH, WHI CCC, WHI Regional Centers, and WHI and VITAL investigators have worked closely to develop leadership and collaborative infrastructure. The Steering Committee, Ancillary Studies Committee, Publications and Presentations Committees, and other committees will include both WHI and BWH representatives. We expect to include all interested investigators in future projects involving the trial, and in the leadership and conduct of ancillary studies.

15.0. Study Timeline

The study plan assumes that recruitment, placebo run-in and randomization procedures will be completed for all 22,000 participants within 1-3 year of study initiation. This will allow an average of 4 years of intervention and follow-up; and 6 months for trial close-out and analyses (Table 2):

Table 2. Anticipated timeline for completion of the COSMOS trial

Activity	Y1	Y2	Y3	Y4	Y5

Finalize protocol and arrangements for study pills	X
IRB approvals	X
Subject recruitment	X X X
Placebo run-in	X X X
Treatment and follow-up	X X X X X
Biomarker and blood pressure collection	X X X X X
Clinic-based assessments	X X X X X
Study closeout	X
Analyses and publication of final manuscripts	X X

16.0. Ancillary Studies

Ancillary studies to the COSMOS will proceed through the WHI Ancillary Studies Committee approval process. The WHI DCC (Project Coordinator) will provide administrative support as needed for ancillary study committee activities related to this trial.

17.0. Appendix

- COSMOS Consent
- Cover Letter for WHI participants for COSMOS 1
- Cover Letter for non-WHI participants for COSMOS 1
- COSMOS 1 (Screening form)
- COSMOS 2 (Baseline form)
- COSMOS 3 (Post run-in Adherence form)
- COSMOS Food Frequency Questionnaire
- COSMOS 6-Month Questionnaire
- COSMOS 12-Month Questionnaire
- COSMOS 18-Month Questionnaire
- COSMOS 2-Year Questionnaire
- COSMOS Food Frequency Questionnaire 2
- COSMOS 30-Month Questionnaire
- COSMOS 3-Year Questionnaire
- COSMOS 42-Month Questionnaire
- COSMOS 4-Year Questionnaire
- COVID-19 Survey
- June COVID-19 Survey
- August COVID-19 Survey
- COSMOS January 2021 Questionnaire
- COSMOS Obs 1 Questionnaire
- COSMOS Obs 2 Questionnaire
- COSMOS Obs 3 Questionnaire

The **CO**coa **S**upplement and
Multivitamin **O**utcomes **S**tudy
(COSMOS)
Statistical Analysis Plan

Investigators:

[name], DrPH and [name], MPH, Brigham and Women's Hospital

[name], Fred Hutchinson Cancer Research Center

February 4, 2022

ClinicalTrials.gov Identifier: NCT02422745

Infrastructure support provided by an investigator-initiated grant from Mars Symbioscience.

Cocoa Extract supplements and matching placebo provided by Mars Symbioscience.

Multivitamins and matching placebo provided by Pfizer Inc.

Partial infrastructure support provided through the National Heart Lung and Blood Institute's funding for the Women's Health Initiative Clinical Coordinating Center and Regional Center contracts.

COSMOS Statistical Analysis Plan

In this 2x2 factorial trial, the primary aim is to compare the main effects of intention-to-treat with cocoa extract on incident cardiovascular disease (CVD) events, and multivitamins on rates of diagnoses of new cancers. The primary analysis be based on the intention-to-treat principle and use the Cox proportional hazards model for time-to event data(1) and estimate the hazard ratio (HR) for each intervention using indicators for the specific treatment, controlling for the second intervention, and stratifying the baseline hazard by (at minimum) sex, age group, and recruitment center (Women's Health Initiative (WHI) or Brigham and Women's Hospital (BWH)). P-values will be based on a score tests for each intervention HR. Because the cohort consists of older women and men, competing risks due to deaths from other causes will also be incorporated. Specifically, the primary analyses will estimate the cause-specific hazard and HR comparing intervention groups for each outcome by censoring individuals with deaths due to competing causes. We will estimate the cumulative incidence function for each comparison (multivitamin versus placebo, cocoa extract versus placebo) and plot the subdistribution of each endpoint over time.(2, 3)

Cocoa extract-specific analyses

Cox proportional hazards models estimated HRs using an indicator variable for cocoa extract treatment and stratifying the baseline hazard functions by sex, age group, recruitment source, and multivitamin intervention arm. COSMOS was designed for 22,000 participants with $\geq 80\%$ power to detect a 11% relative hazard reduction in total CVD, and $>95\%$ power to detect the same reduction for the secondary outcome of CVD plus all-cause mortality. We also had $\geq 90\%$ power to detect a 14% reduction in total cancer. Models were constructed for each clinical outcome, where person-time for each outcome was counted as days from randomization to the first post-randomization diagnosis of the designated outcome. Follow-up was censored at date of last contact, death, or end of the trial on December 31, 2020, whichever came first.

Kaplan-Meier cumulative incidence curves, cumulative HRs, interactions between randomization groups with trial-time, and analyses that excluded the first 1 and 2 years of follow-up assessed whether treatment effects varied over time (4). Nine subgroup analyses examined effect modification by *a priori* (concurrent multivitamin randomization assignment, sex, age, and use of statins or aspirin) and *post hoc* (history of CVD, smoking status, number of CVD risk factors, and chocolate consumption) factors. Secondary outcomes (n=14) mostly constituted subtypes of CVD or cancer. Statistical significance ($P \leq 0.05$) was assessed with two-sided p-values. We did not adjust P-values or confidence intervals for multiple testing. Consequently, results for secondary outcomes, other outcomes, subgroup analyses, and other analyses should be interpreted cautiously and considered hypothesis generating. At the nominal 0.05 level, we would expect less than one interaction and one secondary outcome to be significant by chance alone.

Per-protocol analyses censored follow-up when the participant discontinued trial pills, began outside non-study use of a cocoa supplement, and/or took <75% of study pills. HRs and 95% CIs were estimated using Cox regression models, weighted by the inverse probability of dependent-censoring for non-compliance (5). Additional analyses compared self-reports of non-monitored outcomes or potential side effects by intervention group. Analyses were performed using SAS 9.4.

Multivitamin-specific data analyses

Baseline characteristics by treatment groups were compared using chi-squared tests of association, a t-test contrasted age at randomization, and Wilcoxon rank-sum tests compared non-normally distributed variables such as body mass index and exercise. Statistical significance ($P \leq 0.05$) was assessed with two-sided p-values. Our primary analyses were based on the intention-to-treat principle for time-to first event data.(1) Cox proportional hazards models estimated HRs using an indicator variable for MVM assignment and stratifying the

baseline hazard functions by sex, age group, recruitment source, and cocoa extract intervention arm. The trial was designed for 22,000 participants with $\geq 90\%$ power to detect a 14% relative hazard reduction in total cancer. Models were constructed for each clinical outcome, where person-time for each outcome was counted as days from randomization to the first post-randomization diagnosis of the designated outcome. Follow-up was censored at date of last contact, death, or end of the trial on December 31, 2020, whichever came first.

Kaplan-Meier cumulative incidence curves, cumulative HRs, interactions between randomization groups with trial-time, and analyses that excluded the first 2 years (for cancer endpoints) or 1 year (for CVD endpoints) of follow-up assessed whether treatment effects varied over time.(4) Ten subgroup analyses examined effect modification by *a priori* (concurrent cocoa extract randomization assignment, sex, age, history of cancer, use of statins or aspirin) and *post hoc* (smoking status, fruit and vegetable intake at baseline, use of dietary supplements or multivitamins prior to randomization) factors. We did not adjust P-values or confidence intervals for multiple testing. Secondary outcomes mostly constituted subtypes of cancer or CVD, and numbered fewer than twenty. Results for secondary and exploratory outcomes and those for subgroup analyses should therefore be interpreted with caution and considered hypothesis generating. At the nominal 0.05 level, we would expect less than one interaction and one secondary outcome to be significant by chance alone.

Per-protocol analyses censored follow-up when the participant discontinued trial pills, began outside (non-study) use of a MVM, took outside (non-study) vitamin D > 1000 IU/day, and/or took approximately $< 75\%$ of study pills (missed > 8 days of study pills per month). Hazard ratios (HRs) and 95% confidence intervals (CIs) were then estimated using Cox regression models, weighted by the inverse probability of dependent-censoring for non-compliance and developed post hoc.(5)

For the biomarker analysis, first we explored the distribution of the biomarkers. The distribution of baseline 25-hydroxy-vitamin D (25(OH)D) ($n = 399$) was mostly symmetric and so

data was analyzed on the untransformed scale. The distribution of baseline vitamin B₁₂ was skewed so data was analyzed on the log-scale. There were 13 participants had vitamin B₁₂ assay values of “>1500” assumed to be above 1500 pg/mL; these values were assigned a value of 1501 pg/mL. For serum folate, 48.9% of the cohort had values explicitly coded as “>22.3” ng/mL at baseline. Therefore, analyses examined the influence of MVM on serum folate coded folate as a binary variable (≤ 22.3 ng/mL vs. > 22.3 ng/mL).

Finally, we compared self-reports of non-monitored outcomes and potential side effects by intervention group. Analyses were performed using SAS 9.4.

References

1. Cox DR. Regression models and life-tables. *J Royal Statist Soc B* 1972;34:187-220.

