6.0. Sample size and power

Power calculations for the primary endpoints of major cardiovascular events and total invasive cancer are based upon a 2x2 factorial trial in approximately 22,000 participants, including 13,000 women aged ≥ 65 years and 9,000 men aged ≥ 60 years. Based on the log-rank test (equivalent to score tests for hazard ratios from a Cox model without covariates), Freedman³⁶ has shown that the power, $1-\beta$, of this test to detect a specified hazard ratio HR based on a two-sided test with significance level α is a simple function of the number of accrued events, m , in the two groups combined: $1-\beta = \Phi(\sqrt{m}(|HR-1|)/(|HR+1|) - Z_{1-\alpha/2})$, where Φ is the standard normal cumulative distribution function. The factorial design of this trial is motivated primarily by efficiency. The scientific justification for testing each intervention is independent of the other and stands alone. Therefore each comparison (multivitamins versus placebo and cocoa extract versus placebo) will be based on a marginal test (but controlling for the other intervention) at a level of $\alpha = 0.05$.

Estimates of study power and the expected numbers of confirmed, accrued events in Table 1 are based on the following assumptions: (1) independent and equal allocation of participants to each treatment; (2) an age distribution based on that observed among WHI women ≥ 65 years and men aged ≥ 60 years responding to the VITAL mailings; (3) annualized age-specific event rates based on observed rates during WHI and VITAL follow-up, adjusted for aging; (4) same event rates for men and women given that women are approximately 5 years older than men; (5) mean trial follow-up of 4 years, with nominal loss to follow-up as seen previously in WHI, VITAL, and mail-based trials by the BWH Division of Preventive Medicine; and (6) an average of 80% compliance. These assumptions remain the same as proposed for our original power calculations for 18,000 participants.

With approximately 22,000 randomized participants, there will be at least 80% power to detect a 11% relative hazard reduction in total CVD, and $>95\%$ power to detect such a reduction in the important composite of total CVD plus all-cause mortality with the expected number of events. Similarly, there would be at least 90% power to detect a 14% reduction in total cancer. Power for key secondary outcomes are highly dependent on the frequency of the events.

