7.1.2. Second Mailing

Each site (CCC and BWH) will send a second mailing to those potential COSMOS participants who remain willing and eligible for the trial after the initial mailing. This packet will contain an expanded cover letter; BWH COSMOS trial consent form; an additional baseline questionnaire with questions on eligibility; demographic,

lifestyle, and clinical risk factors; dietary factors; and a return envelope. The Fred Hutchinson Cancer Research Center (WHI CCC) sends recruitment mailings and the Partners consent form to women they previously enrolled into the WHI.

Participants with any questions before they sign and return their BWH COSMOS informed consent will all be offered the opportunity to call a BWH toll free number and speak with COSMOS research staff or key Investigators as needed. Responses will be returned to the originating sites for evaluation of eligibility. Non-respondents will be sent a repeat mailing within a few months. Those with uncertain eligibility will be contacted by mail or phone to resolve any issues.

Respondents who are willing but not eligible will be sent a brief thank you note after all phases of screening have been completed. The CCC will mail for WHI participants and BWH will mail for non-WHI participants.

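### The primary Cox models adjust for no prognostic baseline covariates beyond the strata, forgoing a small gain in power (about 0.3 to 2 points for CVD under stated assumptions)

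*SAP*

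**What the plan says.** The opening paragraph of the SAP and Protocol section 10.0 both describe the primary Cox analysis as "stratifying the baseline hazard by (at minimum) sex, age group, and recruitment center", so the list of strata is open. The agent-specific sections then close it. The cocoa section fits a treatment indicator, "stratifying the baseline hazard functions by sex, age group, recruitment source, and multivitamin intervention arm". The multivitamin section does the same, with "baseline hazard functions by sex, age group, recruitment source, and cocoa extract intervention arm". No further covariate is named in either model, and neither section lists a covariate-adjusted analysis of the primary outcome.

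The variables exist. Protocol section 7.1.2 describes a pre-randomization questionnaire covering "lifestyle, and clinical risk factors; dietary factors". The SAP's cocoa section uses "history of CVD, smoking status, number of CVD risk factors, and chocolate consumption" as subgroup factors and labels them post hoc. Statin and aspirin use are a priori subgroup factors in both sections, as is history of cancer in the multivitamin section. That section labels smoking post hoc and compares body mass index between groups at baseline.

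Protocol section 6.0 computes power for a log-rank test, described as "equivalent to score tests for hazard ratios from a Cox model without covariates".

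**The concern.** When prognostic variables are left out of a Cox model, the treatment hazard ratio is pulled towards 1 while its standard error hardly changes, so the test statistic shrinks. Age enters only as a group, with minimum ages of 60 and 65 and no upper limit, so age differences remain within strata. Smoking and the count of CVD risk factors do not enter at all.

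Both primary tests look for small effects (11% and 14% reductions), where a point or two of power has some value, and the data are already in hand. Without an adjusted analysis, readers also cannot see whether the result is sensitive to chance imbalance in these variables.

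**Working it through.** **1. Reproduce the plan's figures.** Protocol section 6.0 gives power = Φ(√m·|HR−1|/(HR+1) − 1.96) for a two-sided 5% test, and Table 1 gives the events m.

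- CVD, HR 0.90, m = 2479: √2479 × 0.10/1.90 = 2.621, and Φ(0.661) = 74.6% after rounding up from 74.55% (stated 76%).
- CVD, HR 0.85, m = 2416: 97.9% (stated 98%).
- Cancer, HR 0.85, m = 1790: 92.9% (stated 93%).
- CVD, HR 0.89, events interpolated as 2479 − 0.2 × (2479 − 2416) ≈ 2466: √2466 × 0.11/1.89 = 2.890, and Φ(0.930) = 82.4% (stated at least 80%).
- Cancer, HR 0.86, events interpolated as 1837 − 0.8 × (1837 − 1790) ≈ 1799: 89.1% (stated at least 90%). The gap is no larger than the rounding elsewhere in Table 1, such as 76% against 74.6%.

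**2. A range for prognostic strength.** The documents give none, so every input here is assumed. Let s be the SD of the log hazard within strata that the added covariates capture. For independent covariates, s² is the sum of the following terms:

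| Covariate | Term | Low | High |
|---|---|---|---|
| Current smoking, 5–15%, HR 1.8–2.5 | p(1−p)(ln HR)² | 0.016 | 0.107 |
| Risk-factor count, SD 1, HR 1.2–1.4 | (ln HR)² | 0.033 | 0.113 |
| Other CVD history, 3–10%, HR 2–3 | p(1−p)(ln HR)² | 0.014 | 0.109 |
| Age in bands of 5–10 years, log HR 0.05–0.10 per year | b²w²/12 | 0.005 | 0.083 |
| Sum, and s | | 0.069, 0.26 | 0.412, 0.64 |

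Statin and aspirin use are left out of this sum. SD 0.85 is shown below as a value beyond it.

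**3. Gain from adjustment.** Take a normally distributed log-hazard score with SD s. Set the control hazard so that 4-year incidence matches Table 1's placebo rate: 1 − exp(−4 × 0.030) = 11.3% for CVD and 1 − exp(−4 × 0.022) = 8.4% for cancer. Assume other-cause death at 2 per 100 person-years. Solve for the conditional HR whose Cox limit without covariates equals the planning HR, then multiply the test statistic by ln(conditional HR)/ln(planning HR).

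Example: at s = 0.64, a planning HR of 0.90 corresponds to a conditional HR of 0.8975. The ratio is 0.1081/0.1054 = 1.026, the statistic becomes 2.69, and Φ(0.73) = 76.7%.

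| s | CVD, HR 0.90 (from 74.6%) | CVD, HR 0.89 (from 82.4%) | Cancer, HR 0.86 (from 89.1%) |
|---|---|---|---|
| 0.26 | +0.3 | +0.3 | +0.2 |
| 0.38 | +0.7 | +0.6 | +0.4 |
| 0.50 | +1.3 | +1.1 | +0.7 |
| 0.64 | +2.2 | +1.9 | +1.1 |
| 0.85 | +4.2 | +3.6 | +2.1 |

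Without other-cause death, these limits change by less than 0.1 point.

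**4. Cross-checks for CVD at HR 0.90.**

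- A gamma-frailty approximation has attenuation ln(1+θΛ)/(θΛ), with θ = exp(s²) − 1 and Λ = 0.12. At s = 0.64, θ = 0.506, attenuation is 0.971 and the gain is 2.5 points. At s = 0.26 the gain is about 0.3 to 0.4.
- Simulation of 22,000 participants, 400 runs per setting, gives +1.5, +2.5 and +3.9 points at s = 0.50, 0.65 and 0.80. With other-cause death at 2 per 100 person-years it gives +1.0, +1.8 and +2.9. Monte Carlo error is about 0.3 to 0.5 point. Within each setting the standard error of the log HR is the same with and without the covariate (0.041 without other-cause death), so the gain comes from less attenuation.

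**The case against.** The strongest reply is that nothing is lost. Power was planned for an unadjusted test, the planned analysis is at least that good, and the models stratify on the factors used in randomization (Protocol section 4.5), which is an accepted choice. This stands. A reader might infer that the trial is underpowered, or that the SAP contradicts the protocol. The documents support neither: the CVD target is met, and an open list of strata permits additions without requiring them.

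A reader might also expect gains of 4 points or more for CVD. That needs s of about 0.85. The sum above reaches only 0.64 with every input at its high end, and Protocol section 4.2.2 excludes prior MI and stroke, which narrows what history of CVD can add.

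The last objection is timing. The SAP is dated February 4, 2022, follow-up ended on December 31, 2020, the agent-specific sections are in the past tense, and the biomarker text reports observed baseline values. Several natural covariates are already labelled post hoc. Replacing the protocol's primary model at this stage would be open to challenge. That also stands, and it limits the remedy. It does not remove the case for a labelled adjusted analysis.

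**Conclusion.** The point holds as a modest, inexpensive improvement. It is not an error in the plan. Adjustment would add about 0.3 to 2 points of CVD power at either HR 0.90 or HR 0.89, and about 0.2 to 1 point for cancer, if the covariates capture a within-stratum log-hazard SD of 0.26 to 0.64. At HR 0.90 that is equivalent to about 1% to 5% more CVD events (the squared ratio of test statistics, for example 1.026² = 1.05). The direction of the gain is secure if the covariates are prognostic. Its size depends entirely on the assumed SD, and for cancer on applying the same SD range to a different set of covariates.

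**What to change.** In both agent-specific SAP sections, add one Cox model for the primary outcome that keeps the present strata and adds a fixed covariate list.

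- **CVD:** continuous age, smoking status, number of CVD risk factors, history of CVD, and baseline statin and aspirin use.
- **Cancer:** continuous age, history of cancer, smoking status and body mass index.

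Handle missing baseline values with a missing category or simple imputation, and state which. Say explicitly that the open list of strata is resolved in this way.

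Make the adjusted model primary only if the list is fixed before any treatment comparison is seen. Otherwise keep the protocol's stratified model as primary and report the adjusted one as a labelled supportive analysis. In either case, disclose that the SAP treats history of CVD, smoking and number of CVD risk factors as post hoc subgroup factors.

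The cost is a few lines of SAP text and one extra model per primary outcome. The adjusted HR is conditional on more covariates, so it estimates a slightly different quantity from the stratified HR, and the report should say so.
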